Research Protocol

The effect of acupuncture on hemodialysis patients with restless legs syndrome(RLS)

Version 8-23-2019

Principal Investigator:

Principal Investigator(s): [name]

Institution: CHANGHUA CHRISTIAN HOSPITAL, TAIWAN

Protocol No. : Y_105_0300 / CCH IRB No. : 170217

Date of Approval: Aug 23, 2019

Address: [name]

[contact]

The effect of acupuncture on hemodialysis patients with restless legs syndrome(RLS) study protocol for a randomized crossover trial

I. Study Objectives

To our knowledge, there have been no studies on the impact of acupuncture therapy on RLS in patients undergoing hemodialysis. Therefore, the present study was conducted to determine the effect of acupuncture on the severity of RLS in hemodialysis patients. The study is a randomized crossover trial.

II. Background and Rationale

Restless legs syndrome (RLS), a common sensorimotor movement disorder first described in detail by Ekbom, ranges in severity from merely causing annoyance in the patient to affecting sleep and quality of life severely enough to warrant medical treatment. Remarkable differences in prevalence rates of RLS can be observed across countries and geographic regions. Epidemiological research demonstrates that the prevalence of RLS in adults (18 years or more) ranges from less than 1% in Singapore to approximately 10% in Europe and the United States. In 1995, a uniform diagnosis of RLS was made possible worldwide, based on the criteria proposed by the International RLS Study Group (IRLSSG). According to the most recently revised diagnostic criteria, the four clinical manifestations mandatory for the diagnosis are:

- (1) an urge to move the legs, accompanied or caused by uncomfortable and unpleasant sensations in the legs;
- (2) the urge to move or the unpleasant sensations begin or worsen during periods of rest or inactivity;
- (3) the urge to move or the unpleasant sensations are partially or totally relieved by movement;
- (4) the urge to move or the unpleasant sensations are worse in the evening or night or only occur in the evening or night.

Acupuncture, an ancient Chinese medical therapy used in the prevention and treatment of disease, is another useful method for treating RLS. It involves inserting needles into specific points (acupoints or Xue Wei) on the human body to bring about its therapeutic effects. Conventional science suggests that acupuncture works by neurological, neurohormonal as well as psychological mechanisms, and it is thought to confer an analgesic effect. Several kinds of acupuncture methods, such as body acupuncture, auricular acupuncture, scalp acupuncture, electro-acupuncture, laser acupuncture, acupressure, acupoint injection therapy (injection of drugs into acupoints)

or a combination of the approaches mentioned above, are used in the treatment of RLS.

The mechanism of acupuncture treatment for RLS is still ill-defined. According to our preliminary research, the current practice of acupuncture for RLS is mainly based on principles of Traditional Chinese Medicine (TCM) rather than conventional science. The traditional explanation, based on TCM theory, is that acupuncture restores the balance between Yin and Yang and regulates Qi (the essence) and blood so that integral unity can be maintained and miscellaneous diseases cured.

The development of this disorder in hemodialysis patients is progressive, affecting various physical and psychological dimensions over time. The symptoms of this syndrome are greatly intensified at rest, and are relieved by moving the extremities, especially the legs. In hemodialysis patients, the symptoms mainly occur during dialysis when the patient is at rest and cause discomfort. Evidence suggests that RLS in hemodialysis patients is associated with a risk of cardiovascular disease, osteoporosis, musculoskeletal pain, and increased mortality. In the general population and in patients with end-stage renal disease (ESRD), the potential causes of RLS include anemia, pregnancy, iron deficiency, the dysfunction of dopamine within the central nervous system, a family history of RLS, and peripheral neuropathy. In patients with ESRD, iron deficiency, anemia, and dialysis are predisposing factors that can lead to RLS.

Some clinical trials have examined the efficacy of acupuncture in the treatment of RLS and demonstrated that it was able to alleviate the clinical symptoms. To our knowledge, however, there have been no studies on the impact of acupuncture therapy on RLS in patients undergoing hemodialysis. Therefore, the present study was conducted to determine the effect of acupuncture on the severity of RLS in hemodialysis patients.

III. Procedures

A. Research and Design

Subject Selection/Sample

Inclusion criteria:

- 1) Patients between 18-80 years old diagnosed with RLS in hemodialysis patients according to the diagnostic criteria of the International Restless Legs Syndrome Study Group (11).
- 2) Subjects should have bothersome RLS symptoms, despite best medical therapy
- 3) Subjects should be stable on all RLS medication for at least 4 weeks prior to

enrollment

4) All subjects must be able to read and write in English in order to be able to complete home diary cards and questionnaires.

5) All women of childbearing age must be using an acceptable form of birth control, including abstinence, IUD or intrauterine system in place for at least 3 months prior to screening, subject or partner using barrier method (e.g., condom, diaphragm, or cervical cap) with spermicide from screening through study completion; partner has a documented vasectomy > 6 months prior to Baseline, Stable hormonal contraception (with approved oral, transdermal, or depot regimen) for at least 3 months prior to screening.

Exclusion criteria:

- 1) RLS secondary associated with end stage renal disease, iron deficiency or pregnancy
- 2) Does not have sufficient vision to be compliant with study procedures.
- 3) Any other condition (other than the primary indications), which in the opinion of the investigators might contribute to difficulty complying with the protocol

Study setting

The trials will be conducted at the Changhua Christian Hospital. This study will adhere to the recommendations of the Consolidated Standards of Reporting Trials (CONSORT) [15] to allow for greater completeness, transparency and accuracy of reporting. The protocol for this study has been registered in the Clinical Trials register (ClinicalTrials.gov Identifier: NCT04356794).

Eligibility criteria

Subjects who voluntarily sign a consent form will undergo the trial according to the study design. When a subject is determined to be fit for participation based on inclusion and exclusion criteria, the subject will be randomly assigned to 1 of 2 groups in a ratio of 1:1. One group is the true EA experimental group and the other is the sham EA control group. Each group will receive their treatment 2 times a week for 4 weeks. After 4 weeks of treatment and a 2-week washout period, the control group will switch to the experimental group while the experimental group will switch to the control group. The subjects then undergo the treatment of their new group for another 4 weeks.

Treatment and assessment will be performed independently and the practitioners will not be involved in assessing the outcome of the treatment. The subjects, the outcome assessors and the statistician performing the data analyses will be blinded to the treatment allocation throughout the study.

Ethics

This research protocol adheres to the principles of the Declaration of Helsinki and has been approved by the institutional review boards of the Changhua Christian Hospital (No. : 170217). Informed consent will be obtained from each participant before any treatment is given. All subjects will have the right to withdraw from the study at any time.

Inclusion criteria

The inclusion criteria were as follows:

1. Informed consent to participate in the study;
2. Between the ages of 20 - 80 years;

3. A mean frequency of RLS symptoms during the last 6 months of more than twice per week;
4. A score of at least 20 on the International Restless Legs Syndrome Rating Scale (corresponding to severe RLS, IRLSRS);
5. A history of chronic renal failure treated with regular and continuous hemodialysis for at least 3 months;
6. No acupuncture treatment in the last one month.

Exclusion criteria

The exclusion criteria were as follows:

1. An unwillingness to continue to participate in the study;
2. Vascular access in the leg area, such as an arteriovenous shunt;
3. The presence of peripheral neuropathy and vascular problems in the lower extremities;
4. Currently taking drugs for RLS, such as dopamine agonists, benzodiazepines, opioids, and gabapentin;
5. A history of other motor disorders, such as Parkinson's disease, dyskinesia, and dystonia;
6. With an artificial cardiac pacemaker;
7. Pregnancy or breastfeeding.

B. Measurement/Instrumentation

1) International Restless Legs Severity Scale (12): a 40 point scale measuring severity of restless leg symptoms. Patients are asked to answer a series of 10 questions each of which have values ranging from 0 to 4 and the points are then added. Higher values are associated with more severe symptoms.

2) Insomnia Severity Index: a series of 7 questions assessing quality of sleep, with values ranging from 0 to 28.

3) heart rate variability: HRV is the measure of the inconsistent gaps between each heartbeat and is used as an index for different aspects of psychology. HRV is an index of the influence of both the parasympathetic nervous system and the sympathetic nervous systems.

Outcome measures will be at baseline and at week 4, 10 and 18. Medical history including demographic information and information about alcohol, drug and tobacco use will be collected at the baseline visit. Medications and vital signs will be recorded at each visit. Adverse events will be recorded at week 4, 10 and 18 or as reported by the patients. Anticipated benefits for the subjects in the treatment arms will be attenuation of RLS symptoms and improvement in quality of life and sleep.

Statistical Considerations:*A. Sample Size:*

A total of 112 patients will be accrued to the study with roughly equal allocation to each treatment arm. This sample size will achieve over 90% power to detect a 5 point change in the International Restless Legs Severity Scale for the main effects of acupuncture assuming a standard deviation of 4 within each cohort. Additionally we will have roughly 80% power to detect a potential interaction effect on acupuncture therapy. Every effort will be made to reduce attrition; consent documents will emphasize the importance of complete data and encourage patients to return for the follow-up visit.

B. Randomization:

Patients will be randomized to one of the two treatment options with equal allocation. In an attempt to balance severity across treatment cohorts the randomization scheme will be stratified by baseline severity of RLS symptoms as measured by the International Restless Legs Severity Scale (severe vs. very severe). The randomization scheme will be generated by the study statistician with varying block sizes and uploaded to a web-based randomization program. After the patients eligibility has been confirmed and consent documents signed the research coordinator will randomize the patient to one of the two treatment options via the web-based randomization program. The PI will not randomize patients or have access to their treatment assignments.

C. Analysis plan:

All demographic and baseline characteristics of interest will be summarized both overall and by cohort. Frequencies and percentages will be used to summarize categorical variables and means, standard deviations and other appropriate measures of spread for continuous variables. ANOVA models will be used for testing and to estimate the effects of acupuncture. Sensitivity analyses may be considered to assess the impact of baseline severity and other clinically relevant covariates on the outcomes. We will adjust for multiplicity for all contrasts. Secondary outcomes will be analyzed using a similar approach. Further details will be provided in the Statistical Analysis Plan (SAP). For study-related patient data (case report forms) a unique identifier will be used. Study-related documents will be kept in a locked cabinet in a locked office. A separate list (paper-only) will be made containing the unique identifier and the name of each participant. This list will be kept separate from the study related documents. Study databases will be stored on a password protected computer network in a locked office and kept for 5 years.

IV. Bibliography

References

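### English literacy is required of every subject at a single hospital in Taiwan; no reason is given for English, and applying the rule would narrow the population by an unknown amount

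*Protocol*

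**What the plan says.** Item 4 of the first inclusion list (Protocol, III.A, Subject Selection/Sample) reads: "All subjects must be able to read and write in English". The purpose it gives is the completion of diary cards at home and of questionnaires. Its verb is mandatory, whereas items 2 and 3 of the same list use a softer one.

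The title page gives "Institution: CHANGHUA CHRISTIAN HOSPITAL, TAIWAN", and Study setting says "The trials will be conducted at the Changhua Christian Hospital". No other site is named.

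The objective is stated as: "the present study was conducted to determine the effect of acupuncture on the severity of RLS in hemodialysis patients". It carries no language limit.

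A second inclusion list follows the Ethics paragraph. Its six items cover consent, age, symptom frequency, severity score, dialysis history ("A history of chronic renal failure treated with regular and continuous hemodialysis for at least 3 months") and recent acupuncture. None concerns language.

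Under Measurement/Instrumentation, the International Restless Legs Severity Scale (IRLS) is answered by the patient: "Patients are asked to answer a series of 10 questions each of which have values ranging from 0 to 4". No language version is named for it or for the Insomnia Severity Index (ISI). The sample size section states: "A total of 112 patients will be accrued to the study with roughly equal allocation to each treatment arm".

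**The concern.** An eligibility rule should follow from the question, from safety, or from what is needed to collect the data. Item 4 gives a data-collection reason, but that reason supports literacy in the language of the forms, not English in particular. Nothing in the Protocol says that the forms are in English or that a local-language version is unavailable.

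Two outcomes follow, and neither is wanted. If screening staff apply item 4, patients are selected on a trait that the objective does not mention, the pool at one hospital shrinks, and the result speaks for a subgroup. If staff work from the second list, they may enrol patients who fail a stated criterion, and each of those is an eligibility deviation.

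The language of the IRLS matters beyond recruitment. The score sets entry (at least 20), the randomization stratum (severe or very severe) and the outcome behind the sample size. Item 4 is the only text that bears on which language patients will use.

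**Working it through.** **1. The texts side by side.**

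- First list: English reading and writing required of all subjects, for diary cards and questionnaires.
- Second list: six inclusion items, none on language.
- Site: one hospital, in Taiwan.
- Objective: hemodialysis patients with RLS, no language limit.
- Measurements: IRLS, ISI and heart rate variability. Diary cards appear nowhere in the Protocol except in item 4.

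No sentence says which list governs. If the lists are cumulative, item 4 binds. If the second replaces the first, item 4 has no effect.

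**2. The plan's own figure, for context.** The sample size section claims over 90% power for a 5-point difference with SD 4 and 112 patients, so about 56 per arm. Alpha is not stated; I assume two-sided 0.05 and read the statement as a comparison of two groups.

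- Standard error = 4 × √(2/56) = 0.756.
- Power = Φ(5/0.756 − 1.96) = Φ(4.65) = 0.999998, consistent with over 90%.
- Patients per arm for 90% power = 2 × (1.96 + 1.28)² × 4²/5² ≈ 13.4, rounded up to 14. That is 28 in total, a quarter of 112.

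The language criterion does not enter this calculation.

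**3. Effect on recruitment.** Let f be the share of otherwise eligible patients who read and write English. The Protocol does not give f; every value below is an assumption. Patients needed = 112/f, rounded up; excluded = patients needed − 112.

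| Assumed f | Otherwise eligible patients needed | Excluded by item 4 |
|---|---|---|
| 0.9 | 125 | 13 |
| 0.7 | 160 | 48 |
| 0.5 | 224 | 112 |
| 0.3 | 374 | 262 |
| 0.2 | 560 | 448 |
| 0.1 | 1,120 | 1,008 |

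The range runs from a minor inconvenience to a tenfold requirement, and nothing in the Protocol says where in it this hospital lies.

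**4. Effect on the comparison.** Eligibility is confirmed before the patient is randomized (Statistical Considerations, B). Both sequence groups are therefore drawn from the same restricted pool, and the contrast between true and sham treatment is not distorted. What changes is the population it describes.

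**The case against.** The strongest reply is that the harm is not shown. The Protocol gives no literacy rate, no count of dialysis patients and no recruitment rate. A reader might infer that most local patients would be shut out, or that accrual of 112 is endangered. Neither inference is supported, since both need a literacy figure from outside the Protocol. Nor would a shortfall easily sink the main comparison, given step 2 of the working. The interaction claimed at roughly 80% power has less room, but the Protocol does not define it well enough to check. All of this stands and limits the size of the point.

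A second reply is that a criterion present in one list and absent from the other is not a contradiction, because the lists may be cumulative. That is fair for language alone. It does not rescue item 4: read cumulatively, the criterion applies in full. The cumulative reading is also hard to sustain. The first list excludes RLS associated with end-stage renal disease, while the second requires chronic renal failure on hemodialysis. The lower age limits also differ (18 and 20), and the items on RLS medication sit badly together. These passages must be reconciled in any case. The reply is right that two unreconciled lists are the root defect and that English may not be the most restrictive item in the first list.

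A third reply is that item 4 has a purpose, namely completion of the forms. It does, but the purpose does not call for English.

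**Conclusion.** The point holds as a mismatch between a stated rule and the trial it governs. A mandatory English requirement at a single Taiwanese hospital is not justified anywhere in the Protocol, is not part of the objective, and is absent from the second inclusion list. Applied, it narrows the population to an English-literate subgroup; ignored, it creates deviations.

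The size is unknown. The figures of 125 to 1,120 otherwise eligible patients rest wholly on an assumed literate share of 90% to 10%. A reader might also infer that the trial's result would be biased. It would not be: the restriction acts before randomization, and the power calculation is untouched. What is at stake is generalisability, ease of recruitment and clarity about who may enter. The change is worth making because it is cheap, not because the main comparison is in danger.

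**What to change.** Merge the two eligibility lists into one. In it, replace item 4 with: *able to complete the study questionnaires (and diary cards, if used) in the language version used at the site*. Under Measurement/Instrumentation, name the language version of the IRLS and of the ISI, and state whether diary cards are used at all.

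Fix one mode of administration for all patients and visits. Letting some patients complete the scales alone while others have them read aloud would add measurement variation to subjective outcomes.

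The cost is a short eligibility amendment and a line on the instruments. The one real condition is that suitable local-language versions of both scales are available. The Protocol does not say whether they are, so the sponsor should confirm it before making the change.

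### Exclusion 1) bars RLS associated with end-stage renal disease in a trial of hemodialysis patients with RLS, and two conflicting eligibility lists stand with no rule on which governs

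*Protocol*

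**What the plan says.** Section I, Study Objectives, states that "the present study was conducted to determine the effect of acupuncture on the severity of RLS in hemodialysis patients", and the title names the same population.

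Section III.A then gives eligibility twice.

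- **First list (Subject Selection/Sample).** Inclusion 1) admits "Patients between 18-80 years old diagnosed with RLS in hemodialysis patients". Inclusion 2) asks for bothersome symptoms in spite of best medical therapy, and inclusion 3) for at least 4 weeks of stable RLS medication. Exclusion 1) removes "RLS secondary associated with end stage renal disease, iron deficiency or pregnancy".
- **Second list (Eligibility criteria).** Inclusion 2 is "Between the ages of 20 - 80 years". Inclusion 5 is "A history of chronic renal failure treated with regular and continuous hemodialysis for at least 3 months". Exclusion 3 is "The presence of peripheral neuropathy and vascular problems in the lower extremities". Exclusion 4 removes anyone currently on drugs for RLS. No criterion mentions ESRD-associated RLS or iron deficiency.

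The randomisation sentence under Eligibility criteria reads "When a subject is determined to be fit for participation based on inclusion and exclusion criteria" and names neither list. On what may bring the syndrome about, Section II has this: "RLS include anemia, pregnancy, iron deficiency, the dysfunction of dopamine within the central nervous system, a family history of RLS, and peripheral neuropathy". Its next sentence adds dialysis itself to the factors that predispose patients with ESRD to RLS.

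**The concern.** An exclusion that takes out RLS associated with end-stage renal disease cannot stand beside an objective and inclusion criteria that call for RLS in patients on hemodialysis. The clash lies within the first list, between inclusion 1) and exclusion 1), so it remains even if the second list is ignored.

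The second list does not settle it, because the protocol never says whether that list replaces the first or adds to it. A screener has to choose a list and a reading of exclusion 1). That choice decides who is randomised, which enrolments count as protocol deviations, and to which patients the estimated effect applies.

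**Working it through.** The protocol gives no figure for this point, so the check is mainly a comparison of text. It treats patients on regular hemodialysis for chronic renal failure as having ESRD, as the Background does.

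**Step 1. Exclusion 1) against the stated population.** The wording has two readings.

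- *Plain reading*, resting on the phrase about association with ESRD. The intended participants are on dialysis, which Section II itself names as a factor leading to RLS in ESRD. The exclusion then removes the population that the title, the objective, first-list inclusion 1) and second-list inclusion 5 all require.
- *Narrow reading*, resting on the word *secondary*. Only dialysis patients whose RLS is put down to something else may enter. That is a different population from the one in the objective, and no procedure is given for deciding the cause.

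**Step 2. What the narrow reading leaves.** Section II names six potential causes: anemia, pregnancy, iron deficiency, dopamine dysfunction, family history and peripheral neuropathy. If both lists apply, exclusion 1) bars two (iron deficiency and pregnancy) and second-list exclusion 3 bars one (peripheral neuropathy). Of the named causes, 6 − 3 = 3 remain: anemia, dopamine dysfunction and family history. The text does not say whether anemia in a dialysis patient counts as ESRD-associated. Section II does not present its list as complete, so the count covers the named causes only.

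**Step 3. The two lists side by side.**

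| Point | First list | Second list | Patient treated differently |
|---|---|---|---|
| ESRD-associated RLS | Excluded | No such exclusion | Dialysis patient with RLS linked to ESRD |
| Age | 18–80 | 20–80 | Patient aged 18 or 19 |
| RLS medication | Stable for at least 4 weeks | Current use excluded | Patient on a stable RLS drug |

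That makes at least three points on which one patient can pass one list and fail the other.

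**Step 4. Possible effect on screening.** Let s be the share of hemodialysis patients with RLS whose RLS is judged unrelated to ESRD or iron deficiency. The document gives no value, so every s below is an assumption. On this criterion alone, the number to screen for the planned 112 patients is 112/s:

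- s = 0.10: 112/0.10 = 1120
- s = 0.30: 112/0.30 = 373.3, rounded up to 374
- s = 0.50: 112/0.50 = 224
- s = 1.00: 112/1.00 = 112

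On the plain reading s = 0 and nobody qualifies. Under the second list alone this criterion removes nobody.

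**The case against.** The best defence is that the second list is evidently the working one. It stands under its own heading, Eligibility criteria, and the randomisation sentence opens that same section, so its natural referent is the list that follows. The Randomization section points the same way: its strata are severe and very severe, which cover every patient only if there is a severity floor, and only the second list sets one (a score of at least 20). On that view exclusion 1) is a stray line, and dialysis patients would be enrolled as intended.

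This is good evidence of intent, but it is not a rule. No sentence withdraws the first list, and both stand as current text.

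It can also be said that the other conflicts are softer. The two age ranges applied together give 20–80, and a patient on no RLS drug might be taken to satisfy both medication criteria. That is fair as far as it goes. But nothing says the lists are to be applied together, and a patient aged 18 or 19, or on a stable RLS drug, still gets opposite answers. First-list inclusion 2), which presupposes best medical therapy, also sits badly with a bar on current RLS drugs.

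Finally, the screening figures rest on an unknown share, and the top of the range means no effect. That stands: they show how wide the uncertainty is, and the finding does not depend on them. Nor does the document show that screeners at this single hospital would in fact differ; it only leaves them without a rule.

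**Conclusion.** The concern holds and must be fixed. As written, a stated criterion either removes the trial's target population or replaces it with one defined by a causal judgement that has no rule. The two lists disagree on at least three points, and nothing in the protocol says which governs.

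The effect on enrolment is unknown, because the document gives no share of dialysis patients whose RLS would be judged unrelated to ESRD or iron deficiency. The conclusion rests on the text alone and not on any assumed share. That the second list was probably intended makes the likely practical harm smaller, but it does not remove the contradiction.

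**What to change.** Amend Section III.A as follows.

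- Replace the two lists with one that agrees with the hemodialysis objective, so that ESRD-associated RLS is not both the target and an exclusion.
- State how iron deficiency is handled. The sponsor and investigator should decide this.
- If any exclusion by cause of RLS is kept, give the rule by which the cause is assigned.
- In the same amendment, reconcile the age limits and the RLS medication criteria. Their content is a clinical choice for the sponsor and investigator.
- Make the randomisation sentence refer to that single list.

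The cost is one short protocol amendment and a matching screening form. The planned 112 patients and the visits are unchanged. A further screening check is needed only if iron deficiency is kept as a criterion to be verified.
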